For patients randomized to the experimental condition, the study staff member will arrive at bedside, explain the risk and benefits of the study, and will obtain informed consent. Patients will be advised that standing puts them at risk for a fall, and that they should remain seated for each VR intervention. Next, the study staff member will explain the use of the Samsung VR goggle set, and thereafter will allow the patient to use the device freely for up to 30 minutes at a time. An interval of 10 minutes is suggested for first-time use, but patients will be allowed to continue as long as they are not experiencing any

discomfort or side effects (dizziness, motion sickness, etc.). The study staff member will be present during the initial visit, and will work with hospital staff as necessary to ensure the patient is receiving appropriate clinical care throughout the duration of the intervention.

Salivary cortisol will be collected as an optional procedure twice, pre and post demonstration of VR and the Health and Wellness channel.

Collection Instructions:

1. Do not brush teeth before collecting specimen.
2. Do not eat or drink for 15 minutes prior to specimen collection.
3. Do not use any creams, lotions or steroid inhalers immediately prior to the collection.
4. Collect specimen and record collection time.
5. To use the Salivette:
 - a. Rinse mouth thoroughly with water and discard.
 - b. Remove top cap of container to expose swab.
 - c. Place swab directly under the tongue until well saturated, approximately 1 minute.
 - d. Do not touch swab with fingers.
 - e. Place swab back into its container without touching, and replace the cap.
6. Record collection time, and send appropriately labeled Salivette to laboratory.

If the patient expressed interest in keeping the VR hardware longer, and also reports no adverse effects after using the goggles for a 10-minute test run with study staff present, the VR hardware will be left in the patient room. If VR hardware is lost or damaged, patients will be informed that they will not be held responsible. The patient and/or a member of the patient's family will be shown how to use the device as needed, and will also be shown how to recharge the battery if needed. Most patients will use the VR equipment during an interval when they are not receiving clinical care, and could use an entertaining diversion. Study staff will check daily on the status of the patient by contacting the patient's Primary Care Provider. Patients will be asked to log the time and duration of device usage.

Post-Intervention Procedures:

Study staff will retrieve the VR equipment after the patient is no longer interested in using the goggles, the patient is within 24 hours of discharge, or 20 days have elapsed since beginning participation. Pain ratings and medication usage history throughout the hospital will be retrieved from the EHR by authorized study staff for analysis after patient discharge. All patients will be sampled by the HCAHPS Picker survey to assess patient satisfaction.

Control Group

Concurrently with VR intervention participation, we will collect data from up to 122 inpatients (from all diagnosis groups combined) who will serve as controls for this study, selected using the same eligibility criteria used for this study. We will attempt to match control participants based on age, sex, ethnicity, and admitting diagnosis to reduce random variability in the data, but we will still evaluate this as a

between-subjects comparison. These patients will be actively recruited and consented, and they will only interact with study staff for approximately 45 minutes, including time for consent, review of equipment to be used in the intervention, and recording usage time.

Control Group Intervention and Procedures:

Figure 4. Still image from in-room Health and Wellness. Channel

Control participants will be given similar instructions to those who have participated in the standard VR intervention, except they will be exposed to a “sham” intervention that is part of usual hospital care. They will be offered the chance to participate in the study, and if they consent, they will follow the same *Pre-Intervention Procedures* outlined for VR Intervention participants (a physician will collect heart rate and pain data via chart review). Then, the patient will be shown how to use the in-room Health and Wellness relaxation television channel – called the Health and Wellness Channel (<http://www.healinghealth.com/>). The patient will be encouraged to view the channel for approximately 30 minute intervals during the remainder of their hospital stay. After discharge, the physician will collect heart rate and pain data via chart review.

Study Measures

Pain Ratings

As part of usual care, clinical staff regularly obtain assessments of pain intensity from patients using a Numerical Rating Scale (NRS), usually reported on a 0-10 scale, where 0 is no pain, and 10 is the worst pain imaginable. Previous healthcare studies²¹⁻²⁴ have established that NRS is an acceptable method for unidimensional assessment of pain intensity. In this study, patients will not be asked about pain as part of the study. Instead, pain scores reported to the care provider and entered into the EHR will be used.

VR/TV Usage Monitoring

There is no standardized method for assessing viewing time for VR or other audiovisual experiences, without some form of supervision (e.g., automatic, electronic logging on the viewing device; monitoring by study staff; etc.). Currently, we lack the ability to track both TV and VR viewing times through some automated process, so we will provide patients with activity logs, which they will use to record the start time and duration of any viewing experiences (on TV or VR). We realize this method will introduce reporting error, but this error should be equally distributed across both study groups.

HCAHPS

CSMC collects patient satisfaction data using the HCAHPS Picker survey, administered by a third party. In accordance with regulations guiding this survey of patient care experiences, we will not directly influence responses in any way. Instead, we will sample 100% of all study participants, expecting a

response rate of approximately 25%. We will use these data to estimate changes in satisfaction associated with exposure to the intervention condition, versus the control condition. The HCAHPS survey has demonstrated face validity in previous studies.²⁸

Salivary cortisol assay (OPTIONAL):

The salivary cortisol assay will be processed at the lab at CSMC which is then shipped to Quest Diagnostics. It is stable at room temperature for 5 days. The assay is performed using liquid chromatography/tandem mass spectrometry. While cortisol has a diurnal variability with levels highest in the early morning, we will be assessing percent change of cortisol levels over the 10 minutes of the VR demonstration or Health and Wellness channel viewing in each individual. This will minimize the effect of the diurnal variation.

Data Collection

We will collect the following information about VR intervention and Control participants:

- Name and Medical Record Number (secured and stored separate from all other data below)
- Age
- Sex
- Race/Ethnicity
- Admitting Diagnosis during inpatient stay
- ISP ward
- Previous diagnoses of epilepsy and other neurological or visual impairments.
- All Pain ratings throughout the hospital stay.
- All opioid and non-opioid pain medication usage information (dosage amount and timing).
- HCAHPS Patient Satisfaction Picker Survey responses.

Demographic and descriptive clinical data will be abstracted by [name] or authorized study staff at the time of patient selection, and vital signs will be collected before and after the intervention.

Analysis Plan:

The current study plan allows us to enroll an average of three patients per week at a minimum.

We will calculate descriptive statistics for patients in each group. We will then perform bivariate analyses to compare mean cumulative pain scores, morphine milligram equivalents, and average length of stay between groups using t-tests. We will compare the proportion with an opioid complication between groups using chi-squared, and calculate the “number needed to treat” in order to prevent one additional complication with VR vs. no usual care. We will then perform multivariable linear regression analysis to predict pain scores while controlling covariates, including age, demographics, comorbidities, and baseline pain scores. We will report both intention-to-treat analyses including all evaluable patients

by randomized allocation, and per-protocol analyses limited to just those patients in the intervention arm who opt to use VR (while accounting for dose-response potential). We will adopt a P-value of <0.05 as evidence for statistical significance, and calculate 95% confidence intervals around point estimates. All analyses will be performed using Stata for Windows (StataCorp, College Station, TX).

We have powered this study based on our previous research on pain management with VR¹⁸⁻²⁰, which reported clinically meaningful shifts of approximately 1 SD in self-reported pain scores following brief exposure to VR. Several previous studies²¹⁻²³ have established that the minimal clinically important difference on patient-reported pain rating scales (visual analog or numerical ratings) is approximately 13% (approximately 1.4 points on a 0-10 scale, with a standard deviation of 14%). Thus, we are interested in measuring a 1SD change in pain ratings following exposure to the VR intervention, but we will collect a sufficiently large sample to measure smaller changes both within patients exposed to VR, and in comparison to a control group. For all analyses, we will assume a 5% Type I error rate (alpha) and a 20% type II error rate (or 80% power). For **within group analyses**, we would require a minimum of 10 patients to detect a 1 SD change in pain scores. However, we have powered the study to detect a 0.38 SD difference **within each group** (with 58 patients per group), however have modified this to 80 patients per group. We used this method to calculate and justify the required sample size for a complete cohort of orthopedic patients. Therefore, the overall intervention and control groups, along with the orthopedic subgroup will be adequately powered for analysis. The sample-size modification is required due to over-estimation of adherence, and aims to support a "per-protocol" analyses. We plan on conducting this per protocol analysis among treatment-compliant subjects *in addition* to the intent to treat analysis. The additional subjects, then, will bring the total N of the per-protocol analysis into a range capable of detecting the hypothesized effect-size used in the original sample-size calculation. While sample-size re-estimation based on observed difference with a limited number of subjects may be biased and misleading, we feel that the goal of the trial (determining efficacy rather than effectiveness) - coupled with the fact that randomization procedures will remain unchanged - supports the request.

For **between group analyses**, we will compare pain scores obtained from all inpatients exposed to the VR intervention to a **80-patient control group**. We expect the variability in pain scores to be comparable to that observed in VR intervention participants (approximately 1 SD change over a 20-minute period, equivalent to an effect size of 1.0), so we are collecting data from the same number of patients (80) with complete data in Phase 2. We have powered this study to detect an SD difference as low as 0.52 between the VR intervention and control participants (requiring 80 patients in each group).

We will conduct an exploratory **subgroup analysis** to detect changes in salivary cortisol between patients exposed to VR vs patients exposed to the control intervention.

As of September 2017, 9 patients have been consented to participate in this sub-study, but only 1 patient yielded sufficient quantity of samples for a pre- and post-intervention cortisol analysis. The majority of samples were of inadequate quantity for laboratory analysis. Given that all participants eligible to participate in the main study are also eligible for this sub-study, each patient consenting to the main study will be asked to participate in the cortisol sub-study. Accounting for attrition and the

technical complexities of cortisol sampling that often results in low yield quantities, we will recruit 113 patients total (including the 9 that have already been consented as of September 2017).

Risks and Benefits:

Benefits:

To Individual: Patients will likely enjoy using the VR interventions, which are immersive and impressive upon cursory use. We anticipate that patients may report greater satisfaction, pain management, and overall health during the study.

To Society: This will be one of the first RCTs conducted on inpatient use of VR for pain management. Knowledge gained could be used to improve patient satisfaction with care and pain management across all hospitals.

Risks:

Patients using the virtual reality intervention may experience side effects common to users of VR and individuals who view 3D video, including motion sickness, dizziness, eye strain, headaches, or other visual abnormalities. If patients experience these symptoms, they will be asked to stop using the VR software for 15 minutes, and will be allowed to continue *if* they agree and wish to proceed. A small number of patients (up to 0.025%) may experience seizures or severe symptoms (e.g., disorientation, nausea, or drowsiness) upon viewing the virtual reality experience. Seizures from flashing light are more common in children and epileptic patients (who are excluded). To minimize this concern further, we have *not* incorporated flashing lights into the VR experiences. Some patients may find the VR goggles uncomfortable to wear or confining. To date, patients with claustrophobia have *not* reported discomfort using VR goggles, as they are often used in treatment of that condition. Nevertheless, individuals previously diagnosed with claustrophobia should discontinue use if they feel uncomfortable. A trained study staff member will be on hand during initial use to ensure patient safety. Patients who use the VR headset over several days are instructed to use it for a maximum of 30 minutes at a time. In pilot testing, patients have not reported any adverse effects from extended use of VR hardware.

Subjects may feel uncomfortable or embarrassed when answering survey questions. If subjects are uncomfortable or embarrassed answering any survey question, they may skip it. The survey will be labeled with a unique study number so that only the research team can recognize subjects.

Data Security and Privacy:

Data will be abstracted from the EHR by approved staff ([name] and other authorized personnel), and will be transmitted securely to study staff. Staff data collection will be limited to variables mentioned previously. Demographic and clinical data, as well as Qualitative Interview responses will be entered into a secure database and stored on secure servers at CSMC. We will not collect Social Security numbers,

and we will use sequential Unique ID numbers to track patients in the study. All collected specimens will be de-identified before they are sent out to Quest Diagnostics for analysis.

Conclusion:

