The study is an RCT that will enroll up to 244 inpatients with diverse diagnoses to test the efficacy of VR for long term pain management as an adjunct to opioid pain medication. We will randomize one group of patients to receive a VR-based intervention, and the other group of patients will receive a control “sham” intervention. We will randomize patients using the MS Excel random number generator to ensure that there is an equal distribution of participants in the control vs. experiment group. We will measure changes in self-reported pain, opioid pain medication usage (including breakthrough pain), time between doses, and other characteristics of the hospital visit. We will also assess patient satisfaction after 6 weeks using the HCAHPS survey. We will assess pre and post changes in pain between both the VR and control groups.

Originally, study participants were selected by an Investigator (Drs. [name], [name], [name], [name], [name], [name], [name], [name], [name], [name], [name], or [name]) and any other CSMC physicians who wished to refer their patients who met inclusion criteria. In the next phase of the study when the focus turns to orthopedic patients, CSMC physicians [name] and [name] and any other CSMC orthopedic physician will identify and refer orthopedic patients who meet inclusion criteria to participate in this trial. During the VR Intervention, we will place VR hardware on patients in their rooms, and allow

patients to use VR software for a 10-minute trial run. If they are interested, patients will be allowed to continue to use the VR software as needed for the remainder of their hospital stays. During the control “sham” intervention, patients will be instructed on the use of the in-room television system, and then shown 10 minutes of the Health and Wellness CARE Channel; these patients will be encouraged to repeat viewing as needed during the remainder of their hospital stays.

VR Intervention

[figure not shown]

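### Controls are to be matched where possible on four factors, yet three outcomes get no adjusted analysis and the pain model does not name admitting diagnosis; if matching works, the unadjusted tests are conservative

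*Combined protocol and SAP*

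**What the plan says.** The Control Group section states the intention, its purpose and the analysis in one sentence: an attempt will be made to match controls on age, sex, ethnicity and "admitting diagnosis to reduce random variability in the data, but we will still evaluate this as a" between-subjects comparison. No pairing rule, ratio or matched-pair allocation is described. Elsewhere allocation is random; under Overview and Study Design the wording is "We will randomize patients using the MS Excel random number generator to ensure that there is an equal distribution of participants" in the two arms.

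The Analysis Plan specifies the following between-arm analyses:

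- Bivariate tests of means: "compare mean cumulative pain scores, morphine milligram equivalents, and average length of stay between groups using t-tests".
- Opioid complications: "We will compare the proportion with an opioid complication between groups using chi-squared", followed by a number needed to treat.
- One adjusted model, for pain only: "We will then perform multivariable linear regression analysis to predict pain scores while controlling covariates, including age, demographics, comorbidities, and baseline pain scores".

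Morphine equivalents, length of stay and complications have no adjusted analysis. Age, sex, race/ethnicity and admitting diagnosis are all in the Data Collection list.

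**The concern.** Matching is meant to reduce variability. When two arms are balanced on factors that predict the outcome, the difference between arms varies less from trial to trial. An unadjusted t-test does not know this: its standard error still contains the variation that the matching has removed from the comparison. The interval is then too wide and the test rejects a true null hypothesis less often than 5% of the time. The same mechanism applies in kind to chi-squared.

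A regression that includes the matching factors repairs this without a paired test. The plan has such a regression for pain, apart from admitting diagnosis, and has none for the other three outcomes.

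Diagnosis is also the factor that the plan itself links to pain. The Study Population and Period section moves recruitment to orthopedics because that department supplies patients with severe pain. The full sample will be 160 orthopedic patients and up to 84 others (244 − 160).

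At stake is the precision reported for outcomes named in Aims 1 and 2. The error, where it occurs, is in the conservative direction.

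**Working it through.** **Inputs from the Analysis Plan:** 80 per group, 0.52 SD, 5% alpha (taken as two-sided, which the plan does not state), 80% power. **Assumed:** the between-arm outcome correlation ρ that matching induces. The documents give no value, so 0.1 to 0.3 is shown.

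**The plan's own figure.** n per group = 2(1.960 + 0.842)² / 0.52² = 58.05, so 59. The stated 80 does not reproduce at 80% power; with 80 per group, power at 0.52 SD is 90.8%. That mismatch is a separate matter. It is used here only to fix the baseline.

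**Standard errors, in SD units.**

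- Reported by the unadjusted t-test: √(2/80) = 0.158, whatever ρ is.
- True, if matching works: √(2(1 − ρ)/80).
- Excess width: 1/√(1 − ρ).
- Actual Type I error: 2[1 − Φ(1.96/√(1 − ρ))].
- Power, unadjusted: Φ[(0.52 − 1.96 × 0.158)/true SE].
- Power, adjusted: Φ[0.52/true SE − 1.96].

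Example at ρ = 0.2: the true SE is 0.141. Unadjusted power is Φ(1.486) = 93.1% and adjusted power is Φ(1.717) = 95.7%.

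| ρ (assumed) | True SE | Width ratio | Type I error | Power, unadjusted | Power, adjusted |
|---|---|---|---|---|---|
| 0 | 0.158 | 1.00 | 5.0% | 90.8% | 90.8% |
| 0.1 | 0.150 | 1.05 | 3.9% | 91.9% | 93.4% |
| 0.2 | 0.141 | 1.12 | 2.8% | 93.1% | 95.7% |
| 0.3 | 0.132 | 1.20 | 1.9% | 94.4% | 97.6% |

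The power gap is 1.5, 2.6 and 3.2 points. Reading down the unadjusted column, matching still raises power from 90.8% to between 91.9% and 94.4%.

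**Simulation check** (80 per arm, 8,000 runs, no true effect, ρ = 0.2). With matched arms, the estimate had a true SD of 0.142. The unadjusted t-test reported 0.158 and rejected in 3.0% of runs. Regression on the matching covariate reported 0.141 and rejected in 4.9%.

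**If allocation is simple randomisation.** In the same simulation with unmatched arms and a covariate explaining 20% of the variance, the unadjusted test reported 0.158 and rejected in 5.4% of runs. The adjusted test reported 0.142 and rejected in 5.3%. Both are close to nominal, and the adjusted one is more precise.

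**Limits.** The formulas are for means. The plan gives no event rate for complications, so no figure is offered for chi-squared. The 80 per group and 0.52 SD were set for pain; the plan states no effect size for morphine equivalents or length of stay.

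**The case against.** The strongest reply is that the premise may not hold. Matching is only to be attempted, no pairs are formed, and allocation is by random number generator. If the arms are simply randomised, ρ is about zero and the t-tests and chi-squared keep their nominal error. This stands. It is why the size of the effect is conditional, and why the documents do not support a flat statement that the planned intervals and P values are wrong.

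Three other stronger readings are tempting and also fail:

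- **That matching buys no precision.** The estimate itself becomes less variable, and even the unadjusted test gains a little power. What does not improve is the width of the reported interval.
- **That the whole analysis ignores the matching factors.** Pain, the outcome on which the trial is sized, has a planned regression. It names age, its demographics plausibly cover sex and ethnicity, and its covariate list is open-ended. A between-subjects comparison does not rule out adjustment. For pain, the gap is only that admitting diagnosis is not named; comorbidities are not the same thing.
- **That the power loss is large.** At 0.40 SD the contrast would be 73%, 74% or 75% unadjusted against 76%, 81% or 86% adjusted, but 0.40 SD is not in the plan. At the plan's 0.52 SD the loss is about 1.5 to 3 points.

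It can also be said that the error is conservative and that the remedy is ordinary covariate adjustment. Both are true. They limit the severity but do not remove the reason to make a change that costs so little. How matching can coexist with random allocation is a different and more serious question, which this point does not settle.

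**Conclusion.** The point holds in a limited form. The plan states a precision aim for matching but provides no adjusted analysis for morphine equivalents, length of stay or opioid complications, and it leaves admitting diagnosis unnamed in the pain model.

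If matching succeeds and ρ lies between 0.1 and 0.3, unadjusted intervals for mean outcomes are about 5% to 20% too wide and Type I error falls to between 3.9% and 1.9%. At ρ of 0.1 or less the excess width is about 5% at most. If matching does not take effect, the tests are valid and the loss is only the precision that adjustment would have added. These sizes rest on an assumed ρ and, for power, on the pain sample size. The change is worth making; the trial's validity does not depend on it.

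**What to change.** Amend the Analysis Plan as follows:

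1. **Pain model.** Name sex, ethnicity and admitting diagnosis explicitly beside the covariates already listed. Code diagnosis coarsely. Orthopedic or other serves for the full 244. Within the 160-patient orthopedic cohort that split is constant, so use a coarse diagnosis or procedure grouping there, derived from the admitting diagnosis where possible.
2. **Morphine equivalents and length of stay.** Prespecify linear models adjusted for age, sex, ethnicity and admitting diagnosis as the between-arm analysis. The t-tests can stay as descriptive support.
3. **Opioid complications.** Prespecify a covariate-adjusted (standardised) risk difference with its 95% interval. Its reciprocal gives the planned number needed to treat on the same basis.

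These changes correct the standard errors if matching works and add precision if allocation is simple randomisation, so they need not wait for the matching question to be resolved. The four matching variables are already on the data list. The cost is wording and a few degrees of freedom, provided that diagnosis is kept to a small number of groups; fine coding across the mixed non-orthopedic patients would cost more.

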We will conduct a randomized controlled trial (RCT) of VR non-opioid management vs. a control “sham” intervention for a broad and representative group of medical and surgical patients with pain. Hospitalized patients will receive specialized VR interventions, administered via Samsung Gear headsets, to manage breakthrough pain. Control patients will view content on the in-room Health and Wellness television channel. We will follow patients throughout the course of their hospitalization and monitor outcomes during and after their stays. In addition, we will measure endocrine markers of stress as an optional procedure. Our multidisciplinary team of experts in VR, digital health science, mental health, and pain management will test an intervention that, if effective, could be used in resource-limited environments and serve as an adjunct for patients receiving opioids.

Specific Aims and Hypotheses:

The proposed RCT has the following aims:

1. Assess the relative benefits of using VR versus a control intervention for pain management – including pain scores, usage of pain medication, amount of time between pain medication requests, and complications from opioid pain medication – in a large cohort of hospitalized medical and surgical patients with pain.
2. Assess other characteristics of the hospital stay potentially affected by use of VR usage, including length of stay (LOS), and readmissions.
3. Assess patient satisfaction with general care and pain management following VR usage.

We hypothesize the following regarding these aims:

1. Relative to the control intervention, patients who use VR will report meaningfully reduced pain scores, will require less pain medication (opioid equivalents, and non-opioids), will report fewer opioid complications (e.g., nausea, vomiting, constipation), and will delay requests for breakthrough doses of pain medication.
2. Compared to controls, patients who use VR in the hospital will stay in the hospital for less time, report greater satisfaction with care, and will experience fewer readmissions.
3. Compared to controls, patients who use VR will report greater satisfaction with care, as measured by HCAHPS scores after 6 weeks of patient discharge

Exploratory aim:

1. Assess for reduction in cortisol levels with use of VR

Study Procedures:

Overview and Study Design

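### The pain t-test uses an undefined cumulative score with no common time window, so its result can depend on length of stay, in a direction set by how the score is read

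*Combined protocol and SAP*

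**What the plan says.** The Analysis Plan will "compare mean cumulative pain scores, morphine milligram equivalents, and average length of stay between groups using t-tests". This is the only place where the documents use the term cumulative pain score, and they do not define it.

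The other relevant statements describe which ratings are collected, not how they are scored:

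- Post-Intervention Procedures (experimental group): "Pain ratings and medication usage history throughout the hospital will be retrieved from the EHR by authorized study staff for analysis after patient discharge".
- Data Collection lists "All Pain ratings throughout the hospital stay".
- Pain Ratings: the study takes no ratings of its own; "pain scores reported to the care provider and entered into the EHR will be used". The number and timing of ratings therefore follow usual care and differ between patients.
- Control Group Intervention and Procedures: "After discharge, the physician will collect heart rate and pain data via chart review".

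Specific Aims and Hypotheses predicts that "patients who use VR in the hospital will stay in the hospital for less time". It also predicts that VR patients "will require less pain medication (opioid equivalents, and non-opioids").

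After the t-tests, the Analysis Plan adds a "multivariable linear regression analysis to predict pain scores while controlling covariates, including age, demographics, comorbidities, and baseline pain scores". Its outcome has no stated time point either, and length of stay is not among the named covariates.

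**The concern.** A comparison of pain between arms should answer whether pain was lower. If the score runs over the whole stay and the stay is itself expected to differ by arm, the comparison mixes pain with time in hospital.

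The direction of the mixing depends on a definition that the plan leaves open. Under a total, earlier discharge alone looks like pain relief. Under a whole-stay average, earlier discharge removes later and perhaps milder days, so VR looks worse. Nothing says whether ratings made before the intervention count.

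Two analysts following the plan could therefore report different pain results from the same charts. Study Population and Period already reports a preliminary comparison of pain reduction with the control group, so a definition chosen now could be influenced by data already seen by arm.

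**Working it through.** **The plan's own figure.** The Analysis Plan gives 80 per group for a between-group difference of 0.52 SD at 5% alpha and 80% power. The usual formula gives 2 × (1.96 + 0.84)² / 0.52² ≈ 58, or 59 per group by the t distribution (two-sided). At 80 per group, power for 0.52 SD is about 90%. That mismatch is a separate matter. What counts here is that these power figures rest on a change in pain after brief exposure, not on a cumulative score.

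**Inputs for the illustration.**
- From the plan: 80 per arm, 5% alpha (taken as two-sided), 0.52 SD.
- Assumed: mean NRS 5; lognormal stay, mean 4 days, CV 0.3, 0.5 or 0.8; constant rating frequency; pain independent of stay; between-patient SD of stay-level pain 1.4. The plan quotes an SD of 14% beside its minimal important difference, which is not an SD of whole-stay pain, so 2.0 and 2.5 are shown too.

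**If the score is a total.** Total ∝ mean NRS × length of stay. With equal pain and a 20% shorter VR stay, the mean total falls by 20%.

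The CV of the total is √[(1 + CV²pain)(1 + CV²stay) − 1], with CVpain = 1.4/5 = 0.28. At CV of stay 0.3 this is √(1.0784 × 1.09 − 1) = 0.419. The expected t is about 0.20 / [0.419 × √((1 + 0.8²)/80)] = 0.20/0.060 = 3.3, well above the critical value of about 1.98. Simulation gives the share of trials significant in favor of VR with no pain effect:

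| Stay shorter by | SD | CV 0.3 | CV 0.5 | CV 0.8 |
|---|---|---|---|---|
| 20% | 1.4 | 92% | 67% | 36% |
| 20% | 2.0 | 78% | 56% | 32% |
| 20% | 2.5 | 66% | 49% | 29% |
| 10% | 1.4 | 35% | 20% | 11% |
| 5% | 1.4 | 12% | 8% | 5% |

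The per-patient mean gives about 2.5% in that direction throughout. If pain and stay correlate at −0.3 or +0.3, the first row ranges over 84–98%, 57–79% and 31–46%.

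A 0.52 SD pain effect lowers the mean total by 0.52 × 1.4 / 5 = 14.6%. A stay about 15% shorter with no pain effect does the same.

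**Dilution, with equal stays.** At SD 1.4, power of the total for a 0.52 SD effect is 62%, 38% or 20% (CV 0.3, 0.5, 0.8), against about 90% for the per-patient mean. For a 1 SD effect, the total has 99%, 91% or 64%.

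**If the score is a whole-stay average.** Suppose pain starts at 6 and falls by b points a day in both arms. The average over a stay of L days is 6 − bL/2. Stays of 4 and 3.2 days differ by b × 0.8/2 = 0.4b, so VR looks worse by 0.10 points at b = 0.25 and 0.20 at b = 0.5. In the second case the difference is significant against VR in about 13–14% of trials. A common 48-hour window cuts it to 0.03 or less.

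**Morphine equivalents.** With the same daily dose and a 20% shorter stay, the total per stay is significantly lower for VR in 53%, 39% or 25% of trials (dose CV 0.6). Dividing by days of stay does not solve this. If the dose halves every 1, 2 or 4 days, identically in both arms, the per-day figure is about 16%, 10% or 6% higher for VR (CV of stay 0.5). It is then significant against VR in roughly 8–26% of trials.

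**Can patients complete a window?** From the same lognormal (control mean 4 days, VR 3.2, counted from the start point), the share discharged early (control, VR) is:
- CV 0.5: 0.3% and 1.3% before 24 hours; 11% and 22% before 48 hours.
- CV 0.8: 5% and 10% before 24 hours; 26% and 38% before 48 hours.

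**The case against.** A reader might infer that the plan's pain outcome is a total and is therefore biased toward VR. The documents do not support that. They never say the score is a sum, the word mean could refer to an average within the patient, and they give no stay data. The apparent benefit needs both a total and a real reduction in stay; at a 5% reduction it is small.

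A reader might also infer that the trial will miss its target effect. That carries 0.52 SD from change after brief exposure to another measure, and the SD of 1.4 is an assumption here. The direction holds; the exact percentages do not.

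The t-test is only a first step. Length of stay is reported beside it, a baseline-adjusted regression follows, and Overview and Study Design mentions change from before to after. This stands in part: baseline adjustment is already planned. But none of these passages defines the score or its window, and the regression outcome has the same gap.

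Total morphine equivalents per stay is a legitimate outcome for the stated hypothesis. It simply cannot tell opioid sparing from earlier discharge, and dose per day of stay cannot either when dosing declines.

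A short common window also has a price. The protocol follows patients throughout hospitalization, and a window of about a day narrows the question. That stands, and is why ratings from the rest of the stay need a place in a sensitivity analysis.

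**Conclusion.** The concern holds as a matter of definition: the pain score compared by t-test has no stated form, start or window, and the period from which ratings come may differ by arm. This should be fixed before analysis.

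The effect on the result is conditional. Under a total, earlier discharge can pass for pain relief and variation in stay costs power; under a whole-stay average with falling pain, the error runs the other way. The chance of a spurious finding for VR under a total ranges from about 5% to 92% across the settings shown. It rests on assumed stay data, mean NRS and between-patient SD, so it shows that the choice matters and does not estimate the bias in this trial.

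**What to change.** - **Score.** Replace the cumulative score with the per-patient mean NRS, time-weighted where rating times exist, over a window of equal length in both arms.
- **Start.** Use one start point defined identically in both arms: randomization, with its time taken from study records, or the start of the first session if randomization precedes consent. The choice needs stating because the experimental group's Pre-Intervention Procedures describe consent from patients already randomized.
- **Length.** Choose it from pooled stay data without arm labels, before any further comparison by arm, as a window that nearly all patients complete. This may be only about 24 hours; in the illustration, 48 hours fails that test at CV 0.5 and 0.8.
- **Analysis.** Make the baseline-adjusted regression already in the plan the main pain comparison, with the last NRS before the start point as covariate. Add a mixed model of all ratings by time since the start point as a sensitivity analysis covering the rest of the stay.
- **Morphine equivalents.** Report the total per stay and the total over the same common window. Do not claim that dose per day of stay separates opioid sparing from earlier discharge.

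The cost is SAP wording and some programming, with no new patients. Data Collection lists timing for medication but not for pain ratings, so rating times must be abstracted from the EHR. Pain after the window leaves the main comparison, and some patients will be discharged before it ends, possibly unequally by arm; report those numbers by arm.
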